4.7.2 Subsequent Anticancer Therapy or Procedure

Patients' subsequent anticancer therapies or procedures including systemic therapy, radiation, transplant, or other, along with the start date of new anticancer therapy or procedure will be listed.

4.8 Efficacy Analyses

Efficacy analyses will be based on the Efficacy Analysis Set.

Derived efficacy endpoints and tumor assessment data will be listed.

4.8.1 Overall Response Rate

An objective responder is defined as any patient who had a best overall response (BOR) of CR or PR per RECIST 1.1. Overall response rate (ORR) is defined as the proportion of objective responders.

For the analysis of ORR,

- The category of BOR includes complete response (CR), partial response (PR), stable disease (SD), progressive disease (PD), and inevaluable (NE).
- Overall responses derived for BOR must be assessed on or before the start of subsequent anti-cancer therapy or procedure.
- A BOR of SD requires the patient on-study for a minimum of 35 days after the first dose of study drug. A patient with SD only before this time will be considered as NE.
- For patients who do not have post-baseline assessment due to early clinical progression or death (after receiving study drug), they will be categorized separately from patients with assessments.

Disease control rate (DCR) is defined as the proportion of objective responders and patients with SD at least 35 days after the first dose of study drug.

The ORR and DCR and their 95% two-sided exact CIs will be presented. Time to first response and time to BOR will also be summarized.

BOR will also be presented by indication and by indication at RP2D. In addition, extent of study drug exposure will be summarized according to BOR category.

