5.1 Inclusion Criteria

1. Written informed consent must be obtained prior to any procedures.
2. Male or female patient aged 18 years or older.
3. Pathologic diagnosis of solid tumor malignancy that is locally advanced or metastatic at time of Screening:
 - Part 1 Dose-escalation camidanlumab tesirine as monotherapy:
Selected advanced solid tumors: colorectal, head and neck squamous cell carcinoma, non-small cell lung cancer, gastric and esophageal cancers, pancreas, bladder, renal cell carcinoma, melanoma, triple negative breast cancer, and ovarian/fallopian tube cancer.
 - Part 1 Dose-escalation camidanlumab tesirine in combination with pembrolizumab
Selected advanced solid tumors: colorectal cancer, gastric-esophageal cancer, ovarian/fallopian tube cancer, pancreatic cancer, non-small cell lung cancer, and melanoma.
Note: For colorectal cancer, gastric-esophageal cancer, ovarian/fallopian tube cancer, pancreatic cancers MMR/MSS/MSI status is mandatory. If MMR/MSS/MSI status is not available at signature of the informed consent, the test should be performed before C1D1.
 - Part 2 Dose-expansion camidanlumab tesirine in combination with pembrolizumab:
 - Group 1: One of the indications identified in Part 1, for which at least 1 response (PR or CR) was seen
 - Group 2: Patients with advanced solid tumors and MSI-H/dMMR status, who have received a prior regimen containing a PD-1/PD-L1 inhibitor, for which the best response was CR, PR, or SD \geq 4 months, and then progressed while under treatment with the PD-1/PD-L1 inhibitor-based regimen
Note: A maximum of 4 patients with the same indication will be allowed in this basket group.
4. Patients who are refractory to or intolerant of existing therapy(ies) known to provide clinical benefit for their condition.
5. Patients with advanced/metastatic cancer, with measurable disease as determined by RECIST v1.1 or immune-related Response Criteria (irRC)/ immune-related Response Evaluation Criteria In Solid Tumors (irRECIST)/ immune-related Response Evaluation Criteria In Solid Tumors (iRECIST)/ immune-modified Response Evaluation Criteria in Solid Tumors (imRECIST) as per Investigator discretion.

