The same methods used at Baseline that identify sites of disease should be used uniformly for all subsequent assessments. Response to treatment will be determined by the Investigator as CR, PR, stable disease (SD), or progressive disease (PD) according to RECIST v 1.1. As per iRECIST ([Seymour, 2017](#)), the terminology “immune-” CR/PR/SD (iCR/iPR/iSD) will be used. In addition, confirmation of progression or immune-confirmed progressive disease (iCPD) should be performed as per iRECIST, i.e., 4 to 8 weeks after the first PD assessment or immune-unconfirmed progressive disease (iUPD), unless there is clear clinical deterioration which would prevent such confirmation. If progression is not confirmed, disease assessment should continue as originally planned. Clinically stable patients may at investigator discretion either interrupt or continue treatment until iCPD.

Images will be obtained according to local site imaging requirements and may be provided to Sponsor for independent review as part of comparative analysis if required.

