9.7 Efficacy Analyses

9.7.1 Overall Response Rate

The ORR by RECIST v 1.1 will be defined as the proportion of patients with a best overall response (BOR) of CR or PR. The overall response category will be derived based on response assessment performed on or before the start of subsequent anti-cancer therapy.

The percentage of ORR with its 95% confidence interval (CI) will be presented. In contrast to CR, PR, or PD, a BOR of SD can only be made after the patient is on-study for a minimum of 35 days after the first dose of study drug. Any tumor assessment indicating SD before this time period will be considered as a non-evaluable for BOR if no assessment after this time period is available.

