4.8.2 Duration of Response

Duration of response (DoR) is defined among objective responders (CR or PR per RECIST 1.1) as the time from the earliest date of first response until the first date of either disease progression (based on radiographic or clinical progression at end of treatment [EOT]/end of study [EOS]) or death due to any cause.

The censoring rules for DoR are as follow:

- For patients who are still alive at the time of analysis and without objective evidence of progression, patients will be censored at the last tumor assessment.
- For patients who receive subsequent anti-cancer therapy or procedure prior to disease progression or death, patients will be censored at the last tumor assessment on or prior to subsequent therapy or procedure.
- A sensitivity analysis might be considered: if a clinical disease progression or toxicity is observed without radiographic tumor progression assessment being confirmed, then the patient will be censored at the last tumor assessment.

The DoR will be estimated by Kaplan-Meier method. The median DoR and its 95% two-sided CI will be presented.

DoR will also be presented by indication and by indication at RP2D.

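### Neither the protocol nor the SAP says whether a CR or PR must be confirmed, so as written one investigator-read PR counts toward ORR and can meet the response condition for Group 1

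*SAP*

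**What the plan says.** - **Responder.** SAP 4.8.1: "An objective responder is defined as any patient who had a best overall response (BOR) of CR or PR per RECIST 1.1". Protocol 9.7.1: "The ORR by RECIST v 1.1 will be defined as the proportion of patients with a best overall response (BOR) of CR or PR". Neither mentions a repeat scan or a minimum interval for CR or PR.
- **Time condition on BOR.** It applies to stable disease only. Protocol 9.7.1: "In contrast to CR, PR, or PD, a BOR of SD can only be made after the patient is on-study for a minimum of 35" (the unit is days, counted from first dose).
- **Duration of response.** It starts at first response. SAP 4.8.2: "the time from the earliest date of first response until the first date of either disease progression" or death.
- **Reader.** Protocol 7.3 assigns response to the investigator. Independent image review is optional.
- **Progression.** Protocol 7.3: "confirmation of progression or immune-confirmed progressive disease (iCPD) should be performed as per iRECIST, i.e., 4 to 8 weeks after the first PD assessment", unless clear clinical deterioration prevents it. For analysis, Protocol 9.7.2 and 9.7.3 date progression at its earliest occurrence.
- **Decisions that use response.** Group 1 is an indication "for which at least 1 response (PR or CR) was seen" (Protocol 5.1, criterion 3). Protocol 4.1.1 lets the steering committee add patients of the same indication in Part 1 once one PR or CR is documented. It caps a dose level at 10 patients unless at least 3 of the 10 respond. None of these conditions says that the response must be confirmed.
- **Design.** Open-label, no randomization, no hypothesis testing (SAP 3, 3.2 and 4). ORR is a secondary endpoint.

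**The concern.** A programmer following SAP 4.8.1 literally would count a patient with one PR, then PD at the next scan, as a responder. BOR takes the best of several readings. When few patients truly respond, reading error therefore tends to raise the observed rate, and there is no control arm in which the same error would appear.

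True response may well be rare here. Protocol 1.3.4 reports no CR or PR among 44 monotherapy patients. In that setting one PR carries most of the activity signal. It can also qualify a tumour type for Group 1, which is about 16 of the 30 Part 2 patients. What is at stake is signal-finding and the choice of where to expand. No type I error rate is involved, because nothing is tested.

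**Working it through.** **Sample size in the plan.** Protocol 4.1.1 and 4.1.2 give 48 + 17 = 65 for Part 1 and 16 + 14 = 30 for Part 2. The total of 65 + 30 = 95 reproduces the stated figure. It is a sum of cohort sizes, with no response rate or precision target behind it.

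**Combination patients in Part 1 (derived, not stated).** 65 planned − 44 treated with monotherapy (Protocol 1.3.4) = 21. In monotherapy, 8 of 44 had no post-baseline evaluation. Applying the same share gives 21 × 36/44 ≈ 17 scanned patients.

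**Chance of at least one false PR.** Let q be the probability that a true non-responder is read as PR at least once. It is not in the documents; I assume 1% to 5%. With n independent patients the chance is 1 − (1 − q)^n.

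| q | n = 17 | n = 21 |
|---|---|---|
| 1% | 16% | 19.0% |
| 2% | 29% | 34.6% |
| 5% | 58% | 65.9% |

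For n from 12 to 30 the chance is 11.4% to 26.0% at q = 1% and 46.0% to 78.5% at q = 5%.

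**Check against the trial's own data.** Monotherapy best responses were 11 SD, 23 PD, 2 not evaluable and 8 with no post-baseline evaluation (11 + 23 + 2 + 8 = 44). So there was no PR among 11 + 23 = 34 patients read as SD or PD. The chance of that is 0.98^34 = 50% at q = 2% and 0.95^34 = 17% at q = 5%. The one-sided 95% upper limit for q is 1 − 0.05^(1/34) ≈ 8%. The assumed range is not excluded, but its lower end is better supported.

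**Effect of one false PR on the reported rate (Clopper-Pearson 95% CI).**
- Group 1: 0/16 = 0% (0 to 20.6%) becomes 1/16 = 6.3% (0.2 to 30.2%).
- Group 2: 0/14 = 0% (0 to 23.2%) becomes 1/14 = 7.1% (0.2 to 33.9%).

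**What confirmation would do.** Let r be the probability that a false PR recurs at the confirming scan (also assumed). The per-patient rate becomes q × r. For q = 2% and n = 21, the 34.6% falls to:
- 0.8% if errors are independent (r = q);
- 8.1% if r = 0.2;
- 19.0% if r = 0.5.

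**Whether planned scans suffice.** Protocol 7.3 puts the first two scans at 42 ± 7 and 84 ± 7 days. Their smallest gap is (84 − 7) − (42 + 7) = 28 days. Later combination scans are every 63 ± 14 days. Even with opposite ends of the window on consecutive scans, the gap is 63 − 28 = 35 days. A 4-week rule therefore needs no extra imaging.

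**The case against.** - **Response is defined by reference to RECIST 1.1, which may be meant to bring in confirmation.** This stands as a limit. The absence of a rule is silence, supported by a time condition written for SD only; the plan nowhere states that one scan is enough. If confirmation is intended, the plan should say so.
- **Progression is handled the same way.** A reader might infer a double standard in which progression must be confirmed but response need not be. The documents do not support that. Protocol 7.3 says progression should be confirmed, allows an exception for clinical deterioration, and links this to continued assessment and treatment. DoR and PFS use the earliest progression date. The point therefore does not rest on a contrast with progression.
- **Error works both ways.** A true PR can be read as SD, so it is too strong to say that error can only raise ORR. With true rate p and sensitivity s, the bias is (1 − p)q − p(1 − s). That is positive when p is small, but not always.
- **One PR commits nothing.** The Group 1 condition is a minimum in an inclusion criterion, and adding patients in Part 1 is something the steering committee may do. ORR is secondary and descriptive.
- **Part of the remedy exists.** SAP 4.8 lists tumour assessments, and DoR and time to response are summarized, so a one-scan PR would be visible. That helps a careful reader but does not change the headline rate.

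**Conclusion.** The point holds as a gap in the response definition, worth closing at low cost. As written, a single investigator-read PR enters ORR and can satisfy the only written response threshold for Group 1.

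For q of 1% to 5% and 17 to 21 scanned combination patients, the chance of at least one false PR somewhere in Part 1 is about 16% to 66%, with the lower end favoured by 0 PRs in 34 monotherapy patients. This rests on an assumed q, a derived n and independence between patients.

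A reader might take that range as the chance that Group 1 opens in the wrong tumour type. It is not. It pools all six combination indications, and a false PR misdirects Group 1 only if it, rather than a genuine response elsewhere, decides the choice.

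**What to change.** In SAP 4.8.1, define a confirmed CR or PR as a response seen again at a scan at least 4 weeks later, before progression or new anticancer therapy. Report confirmed ORR with its exact 95% CI beside unconfirmed ORR, overall and by indication.

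The cost is SAP wording and one derived variable, with no added scans or visits. The downside is that confirmed ORR may be slightly lower. It may also miss true responders who leave imaging before a second scan, for example in the 63 ± 14 days after Week 12 on the combination. Showing both rates keeps those patients visible.

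Whether the Group 1 condition and the two Part 1 conditions in Protocol 4.1.1 should require a confirmed response is a separate, optional decision. Those conditions are in the protocol, so changing them needs an amendment under Protocol 11.7, and the choice of indication might then wait for the next scheduled scan.

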4.8.2 Duration of Response

Duration of response (DoR) is defined among objective responders (CR or PR per RECIST 1.1) as the time from the earliest date of first response until the first date of either disease progression (based on radiographic or clinical progression at end of treatment [EOT]/end of study [EOS]) or death due to any cause.

The censoring rules for DoR are as follow:

- For patients who are still alive at the time of analysis and without objective evidence of progression, patients will be censored at the last tumor assessment.
- For patients who receive subsequent anti-cancer therapy or procedure prior to disease progression or death, patients will be censored at the last tumor assessment on or prior to subsequent therapy or procedure.
- A sensitivity analysis might be considered: if a clinical disease progression or toxicity is observed without radiographic tumor progression assessment being confirmed, then the patient will be censored at the last tumor assessment.

The DoR will be estimated by Kaplan-Meier method. The median DoR and its 95% two-sided CI will be presented.

DoR will also be presented by indication and by indication at RP2D.

4.8.3 Duration of Stable Disease

Duration of stable disease (DoSD) is defined among patients of SD per RECIST 1.1 as the time from first dose of study drug until disease progression (based on radiographic or clinical progression at end of treatment [EOT]/end of study [EOS]) or death due to any cause.

The censoring rules for DoR in Section 4.8.2 apply to DoSD.

The DoSD will be estimated by Kaplan-Meier method. The median DoSD and its 95% two-sided CI will be presented.

DoSD will be presented by dose, by indication, and by indication at RP2D.

4.8.4 Progression-Free Survival

Progression-Free Survival (PFS) is defined as the time from first dose of study drug until disease progression (based on radiographic or clinical progression at end of treatment [EOT]/end of study [EOS]) or death due to any cause, whichever occurs first.

The censoring rules for PFS are as follow:

- For patients who are still alive at the time of analysis and without objective evidence of progression, patients will be censored at the last tumor assessment.

- For patients who receive subsequent anti-cancer therapy or procedure prior to disease progression or death, patients will be censored at the last tumor assessment on or prior to subsequent therapy or procedure.
- For patients who have no post baseline tumor assessment, and have no disease progression or death, or receive subsequent anti-cancer therapy or procedure(s), patients will be censored at the first dose date of study drug.
- A sensitivity analysis might be considered: if a clinical progression or toxicity is observed without radiographic progression assessment being confirmed, then the patient will be censored at the last tumor assessment.

The PFS will be estimated by Kaplan-Meier method. The median PFS and its 95% two-sided CI will be presented.

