7.3 Efficacy Assessments

Disease assessments will occur as per SoE (Table 1 and Table 2) until progression.

Imaging performed within 4 weeks prior to C1D1 can be accepted as the Screening (Baseline) assessment.

During the treatment period, imaging will be performed 6 weeks (42 days \pm 7 days) after C1D1, but prior to C3D1, and 12 weeks (84 days \pm 7 days) after C1D1, but prior to C5D1, then every 12 weeks (84 days \pm 14 days) until EOT for patients treated with camidanlumab tesirine as monotherapy and every 9 weeks (63 days \pm 14 days) until EOT for patients treated with camidanlumab tesirine in combination with pembrolizumab.

Disease assessments should take place at the timepoints specified even if study drug dosing is delayed.

During the follow-up period, patients who discontinued study drug for reasons other than disease progression or initiation of other anti-cancer therapy will have imaging performed every 12 weeks (84 days \pm 14 days), for patients treated with camidanlumab tesirine as monotherapy, or every 9 weeks (63 days \pm 14 days) for patient treated with camidanlumab tesirine in combination with pembrolizumab, until 1 year from EOT.

If a scan has been performed within 8 weeks of EOT, it does not need to be repeated at EOT.

Additional disease assessments may be obtained, if clinically indicated.

CT or MRI scans with contrast of the chest, abdominal and pelvic area or brain scans (CT or MRI with contrast), and bone scans or X-ray exam if clinically indicated, will be performed. For image acquisition specifications, including instruction in the event of allergy to contrast dye, refer to RECIST v1.1 (Specifications for Standard Anatomical Radiological Imaging).

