4.1.3 Efficacy Analysis Set

All patients who receive at least 1 dose of study drug (refer to Protocol Section 6), have valid baseline disease assessment(s), and at least one valid post baseline disease assessment. Patients who do not have a post baseline assessment due to early clinical progression or death (after receiving study drug) will also be included.

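### SAP 4.8.2 to 4.8.4 count clinical progression as an event, but the first censoring rule, read literally, censors a living patient whose progression is clinical only

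*SAP*

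**What the plan says.** **Event.** SAP 4.8.4 measures PFS from first dose "until disease progression (based on radiographic or clinical progression at end of treatment [EOT]/end of study [EOS", or death. SAP 4.8.2 ends DoR at "the first date of either disease progression (based on radiographic or clinical progression at end of treatment [EOT]/end of study [EOS", or death. SAP 4.8.3 defines the DoSD event in the same terms.

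**First censoring rule.** In both 4.8.2 and 4.8.4 it covers patients "still alive at the time of analysis and without objective evidence of progression, patients will be censored at the last tumor assessment". For DoSD the SAP adds only: "The censoring rules for DoR in Section 4.8.2 apply to DoSD".

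**Third censoring rule, PFS only.** Censoring at first dose begins: "For patients who have no post baseline tumor assessment, and have no disease progression or death". It does not use the word 'objective'.

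**Sensitivity analysis.** As something that might be considered, 4.8.2 and 4.8.4 would censor at the last tumor assessment; the PFS version applies "if a clinical progression or toxicity is observed without radiographic progression assessment being confirmed".

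**Protocol.** The synopsis and Table 3 define progression for DoR and PFS by RECIST v1.1. Protocol 9.7.2 defines DoR by RECIST 1.1. Protocol 9.7.3 does not name RECIST for PFS, and it censors patients who have not progressed, without an 'objective' qualifier. SAP 3.3 declares no modification to the protocol's statistical section.

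**The concern.** The event definition and the censoring rule give different answers for one kind of patient: alive at analysis, with clinical progression and no radiographic progression. Under the definition the patient has an event at the clinical progression. Under the first censoring rule, with 'objective' read as radiographic, follow-up ends at the last scan before it. Two programmers working from the same SAP could report different DoR, DoSD and PFS estimates.

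The literal rule also removes patients just before an event that the SAP itself counts. That is potentially informative censoring, and it generally makes the curves look better. With open-label data, the choice should be fixed before the analysis.

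**Working it through.** The plan gives no figure to reproduce, so the check compares the rules and then looks at direction and size.

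**1. What 'objective' means.** The SAP does not define objective evidence of progression. Its other uses of the word are for objective responders, meaning CR or PR per RECIST 1.1 (SAP 4.8.1, 4.8.2). The radiographic reading is therefore the natural one.

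**2. Apply each rule to a clinical-only progressor.**
- *Alive, scanned, PFS:* an event by definition, censored by the first rule. No other rule resolves it.
- *Alive, DoR or DoSD:* the same conflict. Every responder or SD patient has been scanned, and there is no third rule.
- *Alive, never scanned, PFS:* the third rule censors at first dose only if there is no disease progression, which points to an event.
- *Died before analysis:* outside the first rule, so an event either way. Its date still depends on whether clinical progression counts.

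**3. Which answer was intended.** The sensitivity analysis censors clinical-only progression at the last tumor assessment. If the first rule already did so, the sensitivity analysis would change nothing for living patients of this kind. With the wording of the third PFS rule, this indicates that the main analysis was meant to count clinical progression.

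**4. Can such patients arise?** Protocol 5.4.1 lists clinical progression as a reason to stop study drug. Protocol 7.3 plans follow-up imaging only for patients who stopped for reasons other than progression or new therapy. It also says: "If a scan has been performed within 8 weeks of EOT, it does not need to be repeated at EOT". The waiver is 8 × 7 = 56 days. On nominal dates:
- Weeks 6 to 12: the gap is 42 days, all inside the waiver.
- Combination after week 12: 56/63 = 89% of each interval.
- Monotherapy after week 12: 56/84 = 67%.

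These shares assume that EOT falls on the day of clinical progression. They show when a scan may be skipped, not how often it is.

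**5. Direction (invented data).** Take 16 scanned patients, with four progressions due at each of weeks 12, 21, 30 and 39. One of the week-12 patients instead progresses clinically at week 10, with the last scan at week 6. The median is the first time S(t) ≤ 0.5.
- Counted (16 events): S = 15/16 at week 10, 12/16 at week 12, 8/16 at week 21. Median 21 weeks.
- Censored at week 6 (15 events): S = 12/15 at week 12, 8/15 = 0.533 at week 21, 4/15 at week 30. Median 30 weeks.

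The example sits on the 50% step, so it shows direction and not a typical size. The effect can also reverse. Take three patients: clinical progression on day 80 (last scan day 42), death on day 60, progression on day 100. Counted, S = 2/3 at day 60 and 1/3 at day 80, so the median is 80 days. Censored at day 42, S = 1/2 at day 60, so the median is 60 days.

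**6. Size.** Protocol 1.3.4 reports 44 monotherapy patients: 11 SD + 23 PD + 2 not evaluable + 8 without post-baseline evaluation = 44, so there was no CR or PR. Of the 8, 5 died (11.4%) and 3 had clinical progression: 3/44 = 6.8%, exact 95% CI 1.4% to 18.7%. Those 3 were never scanned, so they cannot enter DoR or DoSD, and in PFS the third rule arguably makes them events. No rate is given for scanned patients or for the combination.

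**The case against.** The strongest reply is that the intent can be recovered. The event is defined first, censoring ordinarily applies to patients without an event, and the sensitivity analysis makes sense only if clinical progression counts. This stands as evidence of intent, and it means the problem is not an open choice of analysis. It does not remove the conflict: a programmer who applies the first rule as written will censor these patients.

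A second reply is that the radiographic reading agrees with the protocol's RECIST v1.1 endpoints, so the SAP's broader event is the departure. That is correct, and it is why the departure should be recorded and the radiographic-only result also reported. The protocol does leave further DoR and PFS details to the SAP, but adding a type of event goes beyond detail.

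Three stronger inferences are tempting and not supported:
- *The Efficacy Analysis Set proves the intent.* SAP 4.1.3 says: "Patients who do not have a post baseline assessment due to early clinical progression or death (after receiving study drug) will also be included". That set also serves ORR and DCR, so keeping these patients says nothing about PFS events.
- *The 6.8% measures the effect.* It comes from unscanned monotherapy patients, who are not the group where the conflict is clearest.
- *The EOT waiver means these patients will go unscanned.* It permits omission. Protocol 7.3 also allows additional assessments when clinically indicated.

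**Conclusion.** The conflict is real and rests on the text. With 'objective' read as it is used elsewhere in the SAP, the first censoring rule overrides the stated event for living patients with clinical progression only. It is clearest for scanned PFS patients and for DoR and DoSD.

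Applied literally, the rule generally lengthens the Kaplan-Meier estimates, though not in every data set. The size is unknown, because it depends on how many scanned patients progress clinically only and are alive at analysis, and the documents give neither number.

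A reader might infer that the trial's conclusions are at risk. The documents do not support that: the primary endpoints are safety endpoints, DoR and PFS are secondary, DoSD appears only in the SAP, and no hypothesis is tested. This is a wording correction worth making before the analysis.

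The undeclared change in SAP 3.3 is a smaller, separate point. It is firm for DoR, where protocol 9.7.2 names RECIST 1.1. For PFS the difference is only from the endpoint definition in the synopsis and Table 3.

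**What to change.** 1. In SAP 4.8.2 and 4.8.4, change the qualifier in the first censoring rule to: without radiographic or clinical progression as defined above. SAP 4.8.3 inherits the change.
2. State which recorded date is used for clinical progression, for example the discontinuation date recorded with that reason. Protocol 5.4 collects a reason and a date of discontinuation, but not explicitly a date of clinical progression.
3. In SAP 3.3, record that the DoR event adds clinical progression to the RECIST 1.1 definition in protocol 9.7.2. In SAP 4.8.4, note that the PFS event is broader than the protocol's RECIST v1.1 endpoint.
4. Make the radiographic-only sensitivity analysis definite, so that the protocol-defined endpoint is also reported. Say there that a death after clinical progression still counts, as it does in the protocol's definitions.

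The cost is one phrase in two sections, a sentence on dating, one entry in 3.3, one note in 4.8.4, and one extra descriptive run per endpoint. If the discontinuation date is used, the protocol already provides for its collection.
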